Flexibility and stretching

Continue all stretching and range-of-motion exercises

L-Bar: External rotation /internal rotation at 90° abduction

Continue capsular stretch

Maintain/increase posterior/inferior flexibility

Strengthening exercises (5-10 repetitions x2.)

- Establish patient on the fundamental shoulder exercises
- Tubing external rotation /internal rotation
- Lateral raises to 90° dumbbell
- Full can dumbbell to 90°
- Side lying External rotation
- Prone horizontal abduction
- Prone extension
- Wall slides
- Biceps/triceps
- Scapular neuromuscular control drills

Guideline for progression to phase 4

- Full, nonpainful range of motion
- No pain or tenderness

Strength test fulfills criteria

- Satisfactory clinical examination

Return to activity phase

Goals

Unrestricted, symptom-free activity

The exercises to be performed at the PT clinic 2 times a week combined with home exercises twice daily.

Any dropouts or participants lost to follow-up will be mentioned with appropriate reasoning.

At the end of the study the data will be collected, coded and tabulated using descriptive and inferential statistics. All analysis will be done using SPSS for Windows (Version 16).

9. Study Duration and Timelines

Total duration of study: 3 years

The treatment protocol will be given for two days per week for twelve weeks.

Each treatment session will be for 45 mins.

Assessment will be done at baseline, 3, 6, 9, and 12 weeks in both the groups.

The treatment protocol will be participant specific and progression will be made according to the participant's performance.

specified timeframes for phase 1 and phase 2

Sr. No.	Task	Timeline
1.	Phase 1: developing and validating the structured exercise program	6 months
2.	Pilot phase	6 months
3.	Phase 2: RCT, implementation of exercise program	18 months

Timeline for the entire study

Sr. No.	Task	Timeline
2.	Related Literature Search	September 2022
6.	Institutional Ethical Committee Approval	October-December 2022
9.	Data Collection Post MRC Approval	February 2023-February 2025
10.	Data Presentation and Analysis	March 2025
11.	Writing Discussion and Conclusion	June 2025
12.	Preparing manuscript and publication	August 2025

10. Informed Consent

The patients who are endorsed in physiotherapy OPD will be approached to consider being a research subjects, Principal investigator will be taking informed consent from the patients. Participants can take 24-72 hours to decide on participation in research. Subjects will be screened for eligibility criteria as per the inclusion and exclusion criteria, Subjects will be enrolled in the study through simple random method.

11. Risk

Potential risks associated with this study are none or very minimal. The time required is 45 minutes is the only discomfort which will be having throughout the study. There is possibility of increase in shoulder pain after exercises which will be managed with pain relieving electrotherapeutic modalities.

The therapist will always be in the vicinity to prevent and treat the same.

12. Outcomes

The effect of structured exercises on pain, range of motion and shoulder functions using Constant Murley score and Shoulder Pain and Disability Index (SPADI) and functional performance using timed functional arm and shoulder test will be tested and compared with conventional exercise program.

13. Data Collection, Management & Confidentiality

a) Indicate below HOW study data will be collected for the proposed research.

√ Study Forms Study Database Study Web-Based/App Other

A standardized data collection tool will be developed. Variables will be designated to measure the pre specified outcomes.

The subject data will be coded by Alphanumeric notations. The subject name and the number will be coded and the subject identifier will be kept locked in the drawer. Subject identifiers- Name, HC number and Date of Birth (DOB) will not be included in the data collection sheet. Subject identifiers will be logged in the subject code and identification list.

Data collection sheet and other confidential documents will be kept inside the cupboard, which will be locked, and only Principal investigator will have the access, which will be limited to the study personal and MRC personal. Only the research team that includes the Principle investigator will have access to the data. In addition, the Medical research Centre will be having access along with the other regulatory bodies in Qatar. The study identifiers will not be shared outside the HMC except the regulatory bodies. Link between the code and Identifier will be stored in the subject code and identification list and will be destroyed after the study finishes. De-identified data will be kept for at least 5 years from the completion of the study.

14. Subject Withdrawal/ Withdrawal of Consent

The subject can request to be withdrawn from the study at any time during the study period. The PI will withdraw the subject & his/ her consent from the study and will notify the research governing bodies of this withdrawal. If subjects sustain any trauma or injury related to shoulder joint or undergoes shoulder surgery, PI may have to withdraw a subject from the study.

15. Statistical Consideration and Data Analysis

Statistical analysis:

Phase 1

In the Delphi method, the results will be analyzed independently in each round. The percentages of responses shall be calculated in categories following the consensus analysis method of most studies that also adopt the visual scale of 1–5, according to CREDES.

The percentages of agreement and disagreement shall be calculated for each of the items in the exercise protocol.

When the percentage is greater than or equal to 80%, the statement is considered to have reached (dis)agreement consensus. The items that reach consensus are excluded from the next round. Finally, those items that have not reached 80% agreement or disagreement will be included to the questionnaires of the following rounds with the modifications proposed by the panelists, if they consider it necessary.

Phase 2

Data collected will be compiled on to a MS Office excel worksheet & will be subjected to statistical analysis using an appropriate package like SPSS software.

Normality of numerical data will be checked using Shapiro – Wilk test or Kolmogorov-Smirnov test. Depending on the normality of data, statistical tests will be determined.

For a numerical continuous data following a normal distribution, inter group comparison (2 groups) will be done using t test, else a non-parametric substitute like Mann Whitney U test will be used.

Descriptive statistics like frequency (n) & percentage (%) of categorical data, mean & Standard deviation of numerical data in each group will be depicted & may be compared using chi square test or a suitable test like Fisher's exact test / McNemar test based on the data obtained.

Intra group comparisons for a numerical continuous data following a normal distribution will be done using paired t test (for 2 observations) or repeated measures ANOVA for >2 observations, else a non-parametric substitute like Wilcoxon signed rank test (for 2 observations) or Friedman's test for >2 observations will be used.

Keeping alpha error at 5% and Beta error at 20%, power at 80%, $p < 0.05$ will be considered statistically significant.

For the primary end-point, namely SPADI score after 12 weeks, and for all other outcomes, a constrained linear mixed model (cLMM) will be applied in order to compare the change from baseline to 12 weeks in experimental and control group.

Principal investigator with the help of bio stastician will be carrying out the data analysis.

16. Adverse Event Reporting

All research related incidents through the OVA/Electronic Incident Reporting System no later than 24 hours for all SAE's covered in the SOP in accordance to Policy OP 4070 REPORTING OF OCCURRENCES, VARIANCES AND ACCIDENTS.

Unanticipated Problems that are serious will be reported to HMC-IRB within 7 days of the investigator becoming aware of the event.

Any other Unanticipated Problems will be reported to HMC-IRB within 14 days of the investigator becoming aware of the event.

17. Ethical Consideration

The study will be conducted in full conformance with principles of the "Declaration of Helsinki", Good Clinical Practice (GCP) and within the laws and regulations of MoPH in Qatar

18. Sponsor, Funding & Collaborator Information

Sponsor and funding: None

This is a PhD study.

The name of the research Centre: PT School and Centre, Seth G.S.Medical College and KEM Hospital, Mumbai, Maharashtra, India

19. Dissemination of Results and Publication policy

The results will be disseminated during PhD presentations at Research Centre as well as at university. Two international publication are mandatory throughout duration of PhD as per the PhD guidelines.

20. References

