Pilot testing of structured exercise program: Pilot testing will be done on 8 patients in experimental group and 8 patients in control group.

Phase 2:

Sample size was determined using the estimates of mean and standard deviation values from literature.

Reference: Debashree Mitra, P.K Mitra et al. Effect of Specific Exercise Program and Conventional Exercise Protocol on Pain and Disability in Patients with Subacromial Impingement Syndrome. International Journal of Health Sciences and Research. 2019; 9 (8):132-139.

Using the formula

$$n = \frac{2 (Z_{\alpha} + Z_{\beta})^2 [s]^2}{d^2}$$

Where Z_{α} is the z variate of alpha error i.e. a constant with value 1.96, Z_{β} is the z variate of beta error i.e. a constant with value 0.84.

Minimally clinical difference was calculated by dividing the individual patient change score by the square root of the SEM. The RCI was considered to confer a true change when it is more than 1.96 (95 % confidence) (the z-score corresponding to the desired level of significance).

(Reference: Allen JC. Sample Size Calculation for Two Independent Groups: A Useful Rule of Thumb. Proceedings of Singapore Healthcare 2011:20(2);138-40)

Approximate estimates:

1. 80% power
2. Type I error to be 5%
3. Type II error to be 20%
4. True difference of atleast 0.31 units between the groups (SPADI)
5. Pooled standard deviation of 0.48

Substituting the values,

$$n = \frac{2 (2.8)^2 [0.48]^2}{(0.31)^2}$$

$$n = 37.31$$

Approximately 38 to 40 subjects / patients per group should complete the study at the endpoint follow up

For follow-up studies, to avoid loss by loss to follow up / attrition, kindly consider recruiting 5-25% more subjects so that even after attrition, we would be able to achieve the required minimum sample size.

Also taking into consideration the attrition to be 15%

$$n = N / (1-0.15)$$

$$n = 38$$
$$(1-0.05)$$
$$= 44.70$$

Approximately 45 subjects / patients per group need to be recruited in the present study

Assessment will be done at baseline, 3, 6, 9, and 12 weeks in both the groups, which will help to detect the changes in outcome measures at frequent intervals.

Out of the five outcome measures,

- Constant Morley part A and SPADI are patient reported scales
- T Fast is functional test
- Constant Murley and Scapulothoracic measurement are ROM assessments

15% attrition is considered while computing the sample size.

7. Study Population and Study Setting/ Location

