Evaluation of the participant will be done at the baseline using Constant Murley Score, shoulder pain and disability Index (SPADI). Shoulder range of motion, shoulder muscles extensibility will be assessed and scapulothoracic ratio will be calculated and documented. T-FAST test will be conducted to score the patients functional performance.

specified timeframes for phase 1 and phase 2

Sr. No.	Task	Timeline
1.	Phase 1: developing and validating the structured exercise program	6 months
2.	Pilot phase	6 months

3.	Phase 2: RCT, implementation of exercise program	2 years
----	--	---------

Outcome measures:

1. Constant–Murley Score

This score is a shoulder-specific assessment tool containing objective measures (range of movement and shoulder strength) and subjective measures (activity of daily living and pain). The maximum is 100 points and indicates excellent shoulder function.

The CMS scale assesses four aspects related to shoulder pathology; two subjective: pain and activities of daily living (ADL) and two objectives: range of motion (ROM) and strength. The subjective components can receive up to 35 points and the objective 65, resulting in a possible maximum total score of 100 points (best function). Pain and ADL are answered by the patient; ROM and strength require a physical evaluation and are answered by the physiotherapist.

Questions and measurements are standardized according to the original description by Constant and Murley.

2. Pain perception

The visual analogue scale (VAS; 0–10) is used to assess the patient’s perceived pain intensity at rest, during arm activity and at night during the previous 24 hours at each follow-up.

3. Shoulder Pain and Disability Index (SPADI)

The Shoulder Pain and Disability Index (SPADI) is a self-administered questionnaire that consists of two dimensions, one for pain and the other for functional activities. The pain dimension consists of five questions regarding the severity of an individual's pain. Functional activities are assessed with eight questions designed to measure the degree of difficulty an individual has with various activities of daily living that require upper-extremity use. The SPADI takes 5 to 10 minutes for a patient to complete and is the only reliable and valid region-specific measure for the shoulder.

4. Timed Functional Arm and Shoulder Test

Description of the Timed Functional Arm and Shoulder Test.

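### Does the sample size fail because the 0.31-unit SPADI difference has no stated scale and two printed figures do not reproduce?

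*Combined protocol and SAP*

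**What the plan says.** In section 6 (Study Methodology), under the Phase 2 sample size calculation, the plan opens with "Sample size was determined using the estimates of mean and standard deviation values from literature" and cites one earlier trial of specific against conventional exercise. It uses the usual two-group formula with z values of 1.96 and 0.84. The inputs, headed as approximate, are "True difference of atleast 0.31 units between the groups (SPADI") and "Pooled standard deviation of 0.48".

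Between the formula and the inputs stands the sentence "Minimally clinical difference was calculated by dividing the individual patient change score by the square root of the SEM", followed by a reliable change criterion of 1.96.

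The printed result is 37.31, taken as 38 to 40 completers per group. Attrition is stated as 15%. The general attrition formula is printed with 0.15, the substituted line with 0.05, and the result as 44.70, taken as 45 per group.

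Section 8 describes the SPADI by its items: five on pain, and for function "Functional activities are assessed with eight questions designed to measure the degree of difficulty". It gives no scoring range, although it does so for the Constant-Murley score and the VAS. Section 15 sets the analysis: "For the primary end-point, namely SPADI score after 12 weeks", using a constrained linear mixed model to "compare the change from baseline to 12 weeks in experimental and control group".

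**The concern.** SPADI at 12 weeks is the primary endpoint, so a reader wants to know what SPADI difference the trial can detect. The text does not say whether 0.31 and 0.48 belong to a total, a percentage or a mean item score, or whether 0.48 is the SD of a score or of a change.

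On a 0-100 or 0-130 total the numbers look odd. Assuming 13 items scored 0-10 (the form is not reproduced in the text), moving one item by one point shifts a 0-130 total by 1.0 and a 0-100 percentage by 100/130 = 0.77. Both exceed the whole 0.31 target.

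The derivation also looks broken. A patient's change divided by the square root of the SEM is a ratio for judging one person, and it does not output a difference between group means. Read literally, it is not even free of units: multiplying every score by k multiplies the index by sqrt(k), which is 3.16 for k = 10.

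With two figures that do not follow from the displayed arithmetic, one could fear that the target of 45 per group has no sound basis, or that a null result could not be interpreted.

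**Working it through.** **Inputs** (section 6, Phase 2 sample size): difference d = 0.31; SD s = 0.48; z sum 1.96 + 0.84 = 2.8; attrition 15%.

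**1. Completers per group.** n = 2 × 2.8² × s² / d² = 2 × 7.84 × 0.2304 / 0.0961 = 37.59. This rounds up to 38, the plan's figure. The printed 37.31 also rounds up to 38.

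**2. Could 37.31 come from unrounded inputs?** Values that round to 0.31 and 0.48 lie in 0.305 to 0.315 and 0.475 to 0.485.
- Smallest n: 2 × 7.84 × 0.475² / 0.315² = 35.7.
- Largest n: 2 × 7.84 × 0.485² / 0.305² = 39.6.
- For example, d = 0.31 with s = 0.4782 gives 37.31.

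So 37.31 is compatible with inputs that were rounded for print.

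**3. Attrition.** 38/(1-0.15) = 44.71, rounded up to 45. 38/(1-0.05) = 40.0. The printed 44.70 therefore used 15%, as stated in the text and in the formula printed just above. In reverse, 45 × 0.85 = 38.25 completers.

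**4. Dependence on scale.** Only s/d enters the formula. If both are rescaled by the same factor, n is unchanged. The implied effect is 0.31/0.48 = 0.646 SD on any SPADI scoring.

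**5. Power at that effect.** Exact unadjusted two-sided t-test at 5%: 79.3% with 38 per group and 81.4% with 40. The difference detectable with 80% power at 38 per group is 0.65 SD.

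**6. Are the inputs impossible?** On a mean item score of 0-10 (same assumed item format), one item moved by one point shifts the score by 1/13 = 0.077. An SD of 0.48 then spans 0.48/0.077, or about six steps. The objection from step size holds for totals and percentages but not for this scoring.

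**7. Score or change?** The constrained model in section 15 sets the baseline means equal. The group difference at 12 weeks and the group difference in change from baseline are then the same quantity, so the target of estimation is not ambiguous. Only the meaning of the SD is open. If 0.48 is the SD of a score, using baseline can only help under this approximation: with an assumed baseline-to-12-week correlation of 0, 0.3, 0.5 or 0.7, power at 38 per group is about 79%, 83%, 89% or 97% (residual SD multiplied by sqrt(1 - r²), 73 degrees of freedom).

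**8. Use of the individual index.** Section 15 contains no responder endpoint and no reliable-change analysis. The index feeds nothing. The plan calls 0.31 a true difference, and the opening sentence attributes the estimates to literature.

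**The case for a change.** The strongest case for a change is that a protocol should stand on its own. A standardised effect of 0.646 says nothing about clinical relevance until it is put in SPADI points. At 0.65 SD, a 0-100 SPADI with an assumed SD of 10, 15, 20 or 25 implies 6.5, 9.8, 13.0 or 16.3 points, a wide range, and the documents do not say where in it the trial sits. The minimal-difference sentence may also lead a reader to think that 0.31 was shown to be clinically important, which the text does not do. The SPADI form is listed as Appendix 4, but even a form showing the item scoring would not say which summary the 0.48 refers to.

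This stands as a comment on reporting. It does not show a wrong sample size. If 0.31 were combined with a larger SD, the required number would be very different: on a 0-10 score with an assumed SD of 1.0 it would be 164 per group. But that replaces one of the plan's inputs with an outside assumption. The plan takes both values as a pair from the literature, and the pair is what fixes the ratio. Nothing in the documents shows that the ratio is wrong.

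**Conclusion.** The observations are correct in substance, but no change to the plan follows.

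- **Missing scale and SD type:** a gap in description. The calculation is scale-free, and analysts can score the SPADI consistently from the form and fit the stated model.
- **Individual-change sentences:** loosely worded, not linked to 0.31 and used in no planned analysis. Removing them would alter no result.
- **37.31 and (1-0.05):** clerical. The first is 0.28 below the displayed substitution and fits rounded inputs. The second is corrected by the text around it.

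Both working figures hold: 38 completers and 45 recruited per group, with 79.3% exact unadjusted power for 0.646 SD. This rests on taking 0.31 and 0.48 as a matched pair on one scale. Whether 0.646 SD is a realistic or worthwhile effect in SPADI points cannot be settled from the documents, so neither adequate power nor a shortfall in those units can be claimed.

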Shoulder pain is the second most common problem among the general population reporting musculoskeletal pain. Values between 6.9 to 26% have been reported for point prevalence and 7 to 67% for lifetime prevalence. The pain is often of long duration and only 50% of patients report recovery after 18 months. Shoulder impingement syndrome (SIS) is responsible for 44% to 60% of medical consultations related to shoulder pain with an approximate prevalence of 70-200 per 1000 adults, which implies a remarkable use of health care resources. The cost for society is high and patients with shoulder disorders account for 20% of all disability due to musculoskeletal disorder¹.

Many terms have been used to describe sub acromial pain and pathology, including sub acromial impingement syndrome, rotator cuff tendinopathy, sub acromial bursitis, supraspinatus tendinosis, and rotator cuff syndrome. The variety in diagnostic labels reflects the uncertainty regarding the pathogenesis. The most common source of pain appears to be the sub acromial bursa and the rotator cuff with the diagnostic label sub acromial impingement syndrome (SIS). SIS refers to the pain that arises when structures in the sub acromial space (primarily the rotator cuff tendons and the sub acromial bursa) are impinged between the humeral head and the acromion mainly during arm activity above the horizontal plane ². This syndrome is a multifactorial condition where intrinsic and extrinsic mechanisms of rotator cuff pathology are the two main factors. The most common deficits are alterations in scapulothoracic kinematics, humeral head displacement within the glenoid cavity and increased elevation and retraction of the clavicle in the sternoclavicular joint during arm elevation.

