The grid of exercise with dosimetry will be constructed as per the experts' opinion in first round of Delphi and will be finalized in further rounds by following TIDieR checklist (Template for Intervention description and replication).

Phase 2: The newly developed structured exercise protocol will be implemented in patients with subacromial impingement syndrome.

Random allocation of subjects who meet inclusion and exclusion criteria and give consent for the study will be allocated to either of the two groups by table of random sequence generation generated by Graph Pad.

Patients will be "randomized" into one of two treatment groups. Patients blinding is not needed, as they will be in either of the group.

- Patients will be put into a group by chance. Neither patients nor the researchers choose which group they will be in. Patients will have equal chance of being placed in a specific group.
- Allocation will be done by an independent person who is not aware of the aim and objectives of the study thus assigning participants into interventional group A and interventional group B.
- Co-investigator will do the follow up assessments hence blinding of principal investigator will be possible.

Group A (Experimental Group) will receive structured exercises for 12 weeks and Group B (control group) will receive conventional exercise program for 12 weeks. The treatment protocol will be given approximately for two days per week for twelve weeks. But the actual treatment frequency and duration after finalization of new protocol. The treatment protocol will be participant specific and progression will be made according to the participant's performance. Assessment will be done at baseline, 3, 6, 9, and 12 weeks in both the groups.

In the literature review, previous studies have mentioned feasible duration of approximately 12 weeks with twice or thrice sessions in a week. However, this will be finalized after development and validation of exercise program with consensus of experts.

The patient's treatment will continue even after 12 weeks if needed.

Type of Study Design: An experimental study.

Sampling Method: Random allocation method

Study Setting: Musculoskeletal Physiotherapy OPD

Duration of study: 3 years

Calculation of sample size-

Phase 1:

Eight to ten experts in the field of shoulder rehabilitation with minimum 10 years of clinical experience will be recruited for Delphi method.

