Study Setting: Outpatient Physiotherapy Units- Orthopedics
Qatar Rehabilitation Institute

Inclusion Criteria

1. Age group between 18-60 years
 2. Symptoms for more than three weeks
 3. Main complaints in the gleno humeral joint region or the proximal arm
 4. Presence of one of the following signs indicating SAIS: Neer impingement test, Hawkins-Kennedy impingement test, painful arc with active abduction or flexion.
- Pain with one of the following resistance tests: external rotation, internal rotation, abduction

Exclusion Criteria

1. Severe pain; pain is > 7/10 on NRS (0 = no pain)
2. Shoulder surgery on affected shoulder
3. Traumatic shoulder dislocation/ fracture within the past 3 months
4. Previous rehabilitation for this episode of shoulder pain
5. Reproduction of shoulder pain with active or passive cervical motion
6. Systemic inflammatory joint disease
7. Global loss of passive shoulder ROM, indicative of adhesive capsulitis
8. Full-thickness rotator cuff tear
9. Incompetent adults
10. Subjects unable to consent
11. patients who are unfit to undergo the suggested exercises as per the protocol.

8. Study procedures

Phase 1: Development of a structured exercise program in patients with sub acromial pain

We will develop and evaluate a structured exercise programs for sub acromial impingement syndrome using an expert consensus with Delphi-based survey technique.

Modified Delphi technique

- Eight to ten experts in the field of Musculoskeletal physiotherapy with focus on shoulder rehabilitation with minimum 10 years of clinical experience will be recruited for Delphi method. Experts are defined as individuals involved in the conception, design, conduct, teaching or analysis of exercise interventions.
- Sixty percent experts will be from physiotherapy discipline and forty percent would be orthopedic surgeons. There are no laypersons.
- Experts who respond to pre-Delphi invitations will be chosen to participate in the first round.
- The participant information sheet will be provided to the experts and consent will be obtained after they are willing to participate.
- Experts will be provided the facility to complete it over several sessions and to allow reviewing their answers before final submission of their responses.

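### Patients may enter at any symptom duration beyond three weeks, but the plan makes no use of duration in allocation or in the primary model: a loss of precision, not a bias

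*Combined protocol and SAP*

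**What the plan says.** - **Entry (Section 7, Inclusion Criteria, item 2).** The criterion is "Symptoms for more than three weeks". No inclusion or exclusion item sets a maximum. Exclusion 4 ("Previous rehabilitation for this episode of shoulder pain") limits earlier care, not duration.
- **Background (Section 3).** The condition is described as slow to resolve: "The pain is often of long duration and only 50% of patients report recovery after 18 months".
- **Allocation (Section 6, Phase 2).** Patients are "allocated to either of the two groups by table of random sequence generation generated by Graph Pad", and "Patients will have equal chance of being placed in a specific group". No blocks, strata or minimisation are mentioned. Section 10 adds "Subjects will be enrolled in the study through simple random method", although that sentence speaks of enrolment.
- **Baseline data (Section 8, Phase 2).** The list covers the outcome instruments, range of motion, muscle extensibility and the scapulothoracic ratio. Symptom duration is not on it. The data collection tool is named as Appendix 1, but its content is not shown.
- **Primary analysis (Section 15, Phase 2).** "For the primary end-point, namely SPADI score after 12 weeks, and for all other outcomes, a constrained linear mixed model (cLMM) will be applied" to compare change from baseline to 12 weeks between the arms. No covariates are listed.

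**The concern.** A patient four weeks into an episode and one two years into it are both eligible, provided neither has had rehabilitation for that episode. By the protocol's own account recovery is gradual and incomplete, so it is plausible that time already spent with symptoms helps to predict SPADI at 12 weeks. If it does, two things follow. Variation that the model could explain stays in the residual, which widens the confidence interval. And with about 45 patients per arm and no stratification, recent and long-standing cases may by chance be split unevenly. If the plan is silent, any adjustment made after such an imbalance is seen will look chosen after the fact. The sample size targets 80% power at the expected number of completers, so modest losses of precision matter.

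**Working it through.** **Inputs from the documents (Section 6, sample size).** Difference 0.31, SD 0.48, z-values 1.96 and 0.84, attrition 15%, 45 recruited per group.

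**Inputs that must be assumed.** The share of recent-onset patients, their advantage at 12 weeks (g, in SD units), and the correlation r of duration with 12-week SPADI after baseline. The planned SD of 0.48 is treated as the residual SD before duration is added.

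**1. The plan's own figure.** 2 × 2.8² × 0.48² / 0.31² = 37.59, so 38 per group (the printed 37.31 is a small slip that leads to the same integer). 38 / 0.85 = 44.7, so 45. The planned sample size is reproduced.

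**2. Power as planned.** Standardised effect 0.31 / 0.48 = 0.646. Standard error with 38 per arm = √(2/38) = 0.229 SD. Power = Φ(0.646/0.229 − 1.96) = Φ(0.855) = 80.4%.

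**3. Gain from adjustment.** Residual variance is multiplied by 1 − r², so power = Φ(2.815/√(1 − r²) − 1.96).

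| Assumption | Residual variance removed | Power, 38 per arm | n needed per arm |
|---|---|---|---|
| r = 0.2 | 4% | Φ(0.913) = 82% | 37 |
| Half recent-onset, g = 0.5 | 0.5² × 0.5 × 0.5 = 6.25% | Φ(0.947) = 83% | 36 |
| r = 0.4 | 16% | Φ(1.112) = 87% | 32 |

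The last column is 37.64 × (1 − r²), rounded up; 37.64 is the plan's formula with unrounded z-values. With a half-and-half split, r = 0.4 needs g = 0.4 / 0.5 = 0.8 SD, so the last row is the optimistic end.

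**4. Chance imbalance.** With 45 per arm and half recent-onset, the SD of the between-arm difference in share is √(2 × 0.5 × 0.5 / 45) = 10.5 points. The normal approximation gives a 34% chance of a gap of at least 10 points and 15% for at least 15 points. Simulating simple randomisation of 90 patients (400,000 draws) gives:

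| Share in one duration category | Gap ≥ 10 points | ≥ 15 points | ≥ 20 points |
|---|---|---|---|
| 20% | 23% | 8% | 2% |
| 30% | 31% | 12.5% | 4% |
| 50% | 34% | 17% | 7% |

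**5. What such a gap does.** A 15-point gap with g = 0.5 shifts the estimate by 0.5 × 0.15 = 0.075 SD, which is 0.075 / 0.646 = 12% of the planned effect (6% to 17% for g = 0.25 to 0.75). Against the standard error it is 0.075 / 0.229 = 0.33, a third of one standard error.

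**6. Type I error.** Simulated over all randomisations (76 patients, g = 0.5 and 0.75), the unadjusted test rejects 5.0% of the time. Conditional on a 20-point gap (half recent-onset, 38 per arm) it rejects 5.4%, 6.4% and 8.2% of the time for g = 0.25, 0.5 and 0.75.

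**7. Cost if duration predicts nothing.** One degree of freedom among 76 completers, about 1/76 = 1.3% of variance. Power stays at about 80%.

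**The case against.** The strongest reply is that nothing here threatens validity. The arms are randomised, concurrent and assessed on the same schedule, so natural recovery occurs in both and cancels in expectation. A reader might infer that wide entry mixes spontaneous recovery with the programme effect. For the between-arm comparison that is not so. Recovery does enter the within-group tests in Section 15, but it would do so whatever the range of durations. The shift from a plausible imbalance is also small, and the confidence interval already allows for it. This stands, and it limits the point to precision.

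Three further objections also stand in part:

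- **Silence is not exclusion.** Section 15 gives the model one sentence and lists no covariates at all, so it does not rule duration out. A constrained model also uses baseline SPADI, which may absorb part of any duration effect. The gap is that no use of duration is specified.
- **Duration may or may not be held.** A reader might infer that the trial already has this variable because it is needed to apply the criterion. The criterion needs only a yes or no at three weeks. Equally, since the content of Appendix 1 is not shown, it cannot be said that duration goes unrecorded.
- **Prognostic strength is undocumented.** The 18-month recovery figure in Section 3 says nothing direct about recovery within 12 weeks by prior duration. The case for the covariate is plausibility set against a very small cost.

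**Conclusion.** The point holds as an inexpensive gain in precision. Eligibility spans a wide range of durations, and the plan assigns duration no role at baseline, in allocation or in the primary model. Under the assumed correlations of 0.2 to 0.4, adjustment is worth about 2 to 6 percentage points of power at 38 completers per arm; the half-and-half, 0.5 SD scenario gives about 2 to 3. If duration turns out to be uninformative, the loss is about 1% of variance. All of these sizes rest on the assumptions stated, since the documents supply neither the mix of durations nor their effect.

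A reader might go further and conclude that the criterion needs an upper limit, or that the estimate will be biased without stratification. The documents support neither. A broad population is a legitimate choice, and chance imbalance does not raise the overall error rate.

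**What to change.** 1. Add symptom duration in weeks to the screening form, if Appendix 1 does not already have it, and to the baseline assessments in Section 8. Report its distribution by arm.
2. In Section 15, pre-specify log(weeks) and its interaction with visit as baseline covariates in the SPADI model. The interaction is needed because baseline SPADI is itself a response in a constrained model: a main effect alone would force duration to act equally at baseline and at 12 weeks. Fix this before any outcome is compared by arm.
3. Leave inclusion item 2 and the 45 per group unchanged.

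The cost is one form field and two model terms. The interaction takes one coefficient if only baseline and 12 weeks are modelled, or four if all five visits enter as categories; Section 15 should say which. Stratified allocation lists by duration are optional. They would need a pre-set category and block size, and the covariate does not depend on them.
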